9.7.1.5 Definitions of Analysis Sets

The safety analysis set will include all subjects who receive at least one dose of study drug and have at least one post dose safety assessment.

The intent-to-treat set will include all randomized subjects who receive study drug.

The per protocol set will include all subjects who sufficiently comply with the protocol. Details of the evaluability criteria will be determined before database lock and treatment unblinding.

The pharmacokinetic (PK) set will include all subjects who receive at least one dose of study drug and have sufficient data to calculate PK parameters.

9.7.1.6 Subject Disposition

Descriptive statistics will be utilized. By-subject listings and summary tables will be provided.

9.7.1.7 Demographic and Baseline Characteristics

Descriptive statistics will be utilized. By-subject listings and summary tables will be provided.

9.7.1.8 Prior and Concomitant Therapy

All investigator terms for medications recorded in the CRF will be coded to an 11-digit code using the World Health Organization Drug Dictionary. The number (percentage) of subjects who took prior and concomitant medications will be summarized on the safety analysis set by treatment group, Anatomical Therapeutic Chemical class, and World Health Organization Drug Dictionary preferred term. Prior medications will be defined as medications that stopped before the dose of study drug. Concomitant medications will be defined as medications that (1) started before the dose of study drug and were continuing at the time of the dose of study drug, or (2) started on or after the date and time of the dose of study drug up to 72 hours after the subject's last dose. All medications will be presented in subject data listings.

9.7.1.9 Safety Analyses

All safety analyses will be performed on the safety analysis set. Safety data, presented by treatment group, will be summarized on an “as-treated” basis using descriptive statistics (e.g., n, mean, standard deviation, median, minimum, maximum for continuous variables; n [%] for categorical variables). Safety variables will include physical examinations, treatment-emergent adverse events (TEAEs), clinical

laboratory parameters, vital signs. Study Day 1 for all safety analyses will be defined as the date of the first dose of study drug.

9.7.1.10 Extent of Exposure

By-subject listings and summary tables will be provided.

9.7.1.11 Adverse Events

The AE verbatim descriptions (investigator terms from the CRF) will be classified into standardized medical terminology using the Medical Dictionary for Regulatory Activities (MedDRA). Adverse events will be coded to the MedDRA lower level term closest to the verbatim term. The linked MedDRA preferred term and primary system organ class (SOC) are also captured in the database.

A TEAE is defined as an AE that emerges during treatment, having been absent at baseline and:

- Reemerges during treatment, having been present before treatment (baseline) but stopped before treatment,

or

- Worsens in severity during treatment relative to the pretreatment state, when the AE is continuous.

Adverse events will be summarized and listed for the safety analysis set. Only those AEs that are treatment-emergent will be included in summary tables. Summary tables will be by treatment group and overall. The incidence (%) will be determined by calculating the number of subjects with at least 1 event and the percentage of subjects with TEAEs by SOC and by preferred term. All AEs, treatment emergent or otherwise, will be presented in subject data listings.

The incidence of TEAEs will be reported as the number (percentage) of subjects with TEAEs by SOC and preferred term. A subject will be counted only once within a SOC and preferred term, even if the subject experiences more than one TEAE within a specific SOC and preferred term. The number (percentage) of subjects with TEAEs will also be summarized by maximum severity (mild, moderate, or severe).

The number (percentage) of subjects with TEAEs will also be summarized by relationship to study drug (possibly related, probably related, and not related).

The number (percentage) of subjects with treatment-related TEAEs will be summarized by SOC and preferred term. Treatment-related TEAEs include those AEs considered by the investigator to be possibly or probably related to study treatment. The number (percentage) of subjects with treatment-related TEAEs will also be summarized by maximum severity (mild, moderate, or severe).

A subject data listing of all AEs leading to death will be provided. Additionally, a subject data listing of all AEs leading to discontinuation from study drug will be provided.

The number (percentage) of subjects with SAEs will be summarized by MedDRA SOC and preferred term for each treatment group. A subject data listing of all SAEs will be provided.

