9.4 TREATMENTS

9.4.1 Treatments Administered

The study drugs will be blinded and assigned to each subject based on the randomization schedule. The contents of each kit will be admixed immediately prior to administration by the investigator who will administer the drug to the patient at no colder than room temperature. The following treatments will be administered as a single dose via urethral catheter:

- URG101 treatment comprises the following:
 - 18 mL containing heparin sodium [REDACTED]
[REDACTED] Lidocaine HCl buffered to pH 7.4 (± 0.2) with 1X [REDACTED]
buffer, [REDACTED] [REDACTED]
[REDACTED]
[REDACTED]
- Placebo treatment comprises the following:
 - 18 mL 1X [REDACTED] buffer (pH 7.4 [± 0.2])
- Heparin treatment comprises the following:
 - 12 mL Heparin Sodium [REDACTED] plus 6 mL
3X [REDACTED] buffer (final mixture buffered to pH 7.4 [± 0.2])
- Lidocaine treatment comprises the following:
 - 12 mL Lidocaine HCl [REDACTED] plus 6 mL 3X [REDACTED] buffer
(final mixture buffered to pH 7.4 [± 0.2])

Prior to administering drug each subject will empty their bladder. Fifteen minutes later (± 5 minutes), the subject will complete the 11-point bladder pain NRS (requires a score of ≥ 5.0 to enter the trial and receive drug) and the 11-point urgency NRS (critical to administer 15 minutes (± 5 minutes) after voiding but no minimum score is required for study entry). These NRS scores will be the baseline scores for pain and

urgency. [REDACTED]

[REDACTED]

[REDACTED]

[REDACTED]

[REDACTED]

[REDACTED]

[REDACTED]

[REDACTED] The study medication is to be left indwelling for 45 minutes, with a minimum of 30 minutes, and after that may be voided by the subject. The test instruments will then be administered at the intervals listed in the schedule of assessments (Table 4).

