9.5.1.10.3 Adverse Events and Other Events of Interest

An AE is any untoward medical occurrence in a subject who is administered an investigational product. An AE does not necessarily have a causal relationship with the study drug.

The criteria for identifying AEs include the following:

- Any unfavorable and unintended sign (including an abnormal laboratory finding), symptom, or disease temporally associated with the use of an investigational product, whether or not considered related to the investigational product
- Any new disease or exacerbation of an existing disease
- Any deterioration in non-protocol-required measurements of a laboratory value or other clinical test (e.g., electrocardiogram [ECG] or x-ray) that results in symptoms, a change in treatment, or discontinuation of study drug
- Recurrence of an intermittent medical condition (e.g., headache) not present pretreatment (baseline)
- An abnormal laboratory test result should be considered an AE if the identified laboratory abnormality leads to any type of intervention, whether prescribed in the protocol or not, and after repeat confirmatory testing has been conducted

A laboratory result should be considered by the investigator to be an AE if it includes the following:

- Results in an intervention, based on medical evaluation (e.g., potassium supplement for hypokalemia)

- Results in any out of range laboratory value that in the investigator's judgment fulfills the definitions of an AE with regard to the subject's medical profile

All AEs observed during the study will be reported on the CRF. All AEs, regardless of relationship to study drug or procedure, should be collected beginning from the time the subject signs the ICF through the last visit. AEs reported prior to randomization will be termed medical history. SAEs will not be considered medical history and will be collected for 72 hours after the last dose.

Abnormal laboratory values should not be listed as separate AEs if the values are considered to be part of the clinical syndrome that is being reported as an AE. Any laboratory abnormality considered to constitute an AE should be reported as an AE on the CRF.

It is the responsibility of the investigator to review all laboratory findings in all subjects and determine if they constitute an AE. Medical and scientific judgment should be exercised in deciding whether an isolated laboratory abnormality should be classified as an AE.

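### As written, the definition of a treatment-emergent adverse event (TEAE) excludes first-ever events after dosing and worsening of ongoing ones, so the TEAE tables would omit new-onset events

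*Combined protocol and SAP*

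**What the plan says.** The definition is in protocol Section 9.7.1.11. It opens: "A TEAE is defined as an AE that emerges during treatment, having been absent at baseline and". Two bullets, joined by *or*, complete it:

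- "Reemerges during treatment, having been present before treatment (baseline) but stopped before treatment"
- "Worsens in severity during treatment relative to the pretreatment state, when the AE is continuous"

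Three rules in the same section govern where events are reported:

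- Tables: "Only those AEs that are treatment-emergent will be included in summary tables".
- Listings: "All AEs, treatment emergent or otherwise, will be presented in subject data listings".
- Serious events: "The number (percentage) of subjects with SAEs will be summarized by MedDRA SOC and preferred term for each treatment group".

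On collection, Section 9.5.1.10.3 includes "Any new disease or exacerbation of an existing disease" among the criteria for an AE, so new events are recorded.

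The synopsis (Statistical Methods) and Section 9.7.1.9 also base the AE summaries on TEAEs, but neither gives its own definition. Section 9.7 refers to a separate SAP. No TEAE definition other than the one in Section 9.7.1.11 appears in the text available.

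**The concern.** The word *and* at the end of the opening clause turns the two bullets into further conditions, when they should be alternatives. Being new since baseline is then not enough for an event to count. It must also have a pretreatment history, which a new event lacks by definition.

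Safety and tolerability is a stated objective (Section 8.2, item 7) and adverse events are a named safety endpoint (Section 9.7.1.3). The TEAE tables are where AE incidence is set out by arm. If the definition is programmed as it stands, the comparison of URG101 with lidocaine, heparin and placebo is made without the events that first appeared after dosing. Incidence would be understated in every arm. The listings would still show the events, but they do not give incidence by arm.

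**Working it through.** The plan has no figure to reproduce here. The check is one of logic. Call the three parts of the definition:

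- A: emerges during treatment and was absent at baseline (opening clause).
- B: was present before treatment, stopped before treatment, and re-emerges (first bullet).
- C: is continuous and worsens relative to the pretreatment state (second bullet).

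The text as written is A and (B or C). The reading that was presumably meant is A or B or C. The table applies both to the possible event histories. The recurrent event has two rows because the result depends on what baseline means.

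| Event history | A | B | C | As written: A and (B or C) | With *or*: A or B or C |
|---|---|---|---|---|---|
| First-ever event after dosing | yes | no | no | not a TEAE | TEAE |
| Earlier event, resolved, recurs; baseline = just before dosing | yes | yes | no | TEAE | TEAE |
| Earlier event, resolved, recurs; baseline = pretreatment period | no | yes | no | not a TEAE | TEAE |
| Ongoing at dosing, worsens | no | no | yes | not a TEAE | TEAE |
| Ongoing at dosing, unchanged | no | no | no | not a TEAE | not a TEAE |

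Three things follow.

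1. **First-ever events.** B and C both need a pretreatment occurrence, so a first-ever event can satisfy neither, whatever baseline means.
2. **Worsening events.** An event that continues from the pretreatment state was not absent at baseline, so A and C cannot both be true. The second bullet can never be met.
3. **Recurrent events.** These qualify only if baseline means the moment just before dosing. The first bullet itself attaches the word baseline to the period when the event was present. On that meaning A and B also conflict, and no history qualifies.

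The table has four distinct histories. As written, one of the four qualifies on one meaning of baseline and none on the other. With *or*, three of the four qualify, and the only one left out is the unchanged ongoing event, which is the usual intent.

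The TEAE-only rule for tables then carries this into the results. New events are collected under Section 9.5.1.10.3, are not classed as TEAEs, and so do not reach the tables by system organ class and preferred term, by maximum severity or by relationship.

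**The case against.** The strongest reply is that this is a plain drafting slip. The opening clause alone already describes a new event, and the bullets read naturally as the recurrence and worsening cases. The literal reading contradicts itself, so a programmer would probably query it. The separate SAP may also carry correct wording. The likely intent is indeed recoverable. But the text available contains no correction, and a programmer would have either to follow it or to depart from it without a documented basis.

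Two stronger readings are tempting, and the documents do not support them.

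- **That new events vanish from the safety report, or from all AE tables.** All AEs stay in the subject listings, and there are separate listings for SAEs, for AEs leading to death and for AEs leading to discontinuation. The sentence on the SAE table is not itself limited to TEAEs. Whether the general TEAE-only sentence governs that table is unclear. INR, aPTT and vital signs are summarized independently of the TEAE rule (Sections 9.7.1.12, 9.7.1.13 and 9.7.1.15).
- **That the treatment period is only the dwell time.** Section 9.4.1 says "The study medication is to be left indwelling for 45 minutes, with a minimum of 30 minutes", and the definition refers to events arising during treatment. Nothing equates the two, and the dwell instruction gives a minimum but no maximum. Follow-up clearly extends further. AEs are collected through the last visit and SAEs for 72 hours (Section 9.5.1.10.3), and a call at 48 to 72 hours asks about AE status (Section 9.1.5). What stands is narrower: the definition gives no end to the treatment-emergent period.

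**Conclusion.** The definition is wrong as written and should be corrected. Applied literally, it classes no first-ever event as a TEAE and can never class a worsening ongoing event as one. Those events would then be left out of the TEAE tables by system organ class and preferred term, severity and relationship. They would remain in the listings, and the SAE table may be an exception.

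The conclusion rests on two assumptions: that Section 9.7.1.11 is the governing definition, and that it is programmed as it reads. If the programmer silently reads *or*, the tables come out as presumably intended, but without support in the text. The size in events cannot be stated, because the documents give neither an expected AE rate nor the share of AEs that would be new-onset.

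**What to change.** Replace the definition with three alternatives and fix the meaning of baseline, for example:

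*A TEAE is an AE with onset or worsening after the start of study drug administration, through the end of the protocol's AE collection period, that (i) was absent before dosing, or (ii) was present earlier, had resolved before dosing and recurs, or (iii) was ongoing at dosing and worsens in severity. Baseline is the state just before dosing.*

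This also replaces the open-ended reference to the treatment period. The window should point to the AE collection period, because the protocol does not state a 72-hour limit for non-serious AEs. Section 9.5.1.10.3 ends their collection at the last visit, Visit 2 may be optional (Section 9.1.4), and the call falls at 48 to 72 hours. The sponsor should therefore say which contact closes the period. It should also say whether the SAE table is limited to TEAEs.

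The cost is essentially one sentence in Section 9.7.1.11, with matching wording in the SAP, settled before database lock and unblinding. No new data are needed. The downside is that reported TEAE rates may be higher than under the literal text.

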Every effort must be made by the investigator to categorize each AE according to its severity and its relationship to the study treatment.

Assessing Severity of Adverse Events:

AEs will be graded on a 3-point scale (mild, moderate, severe) and reported in the detail indicated on the CRF. The definitions are as follows:

Mild	Discomfort noticed, but no disruption of normal daily activity
Moderate	Discomfort sufficient to reduce or affect normal daily activity
Severe	Incapacitating, with inability to work or to perform normal daily activity

The criteria for assessing severity are different than those used for seriousness (see Section [9.5.1.10.3](#), Serious Adverse Events and Other Events of Interest for the definition of an SAE).

The causal relationship of the study drug to an AE will be assessed as related or unrelated, as follows:

Assessing Causality of Adverse Events:

Table 3. Assessment of Causality of AEs

Term	Definition
Definitely related	The AE is clearly related to the investigational agent(s) or research intervention: the AE has a temporal relationship to the administration of the investigational agent(s) or research intervention and follows a known pattern of response, and no alternative cause is present.
Probably related	The AE is likely related to the investigational agent(s) or intervention: the AE has a temporal relationship to the administration of the investigational agent(s) or research intervention and follows a known or suspected pattern of response, but an alternative cause may be present.
Possibly related	The AE may be related to the investigational agent(s) or intervention: the AE has a temporal relationship to the administration of the investigational agent(s) or research intervention and follows a suspected pattern of response, but an alternative cause is present.
Unrelated (or Not Related)	The AE is clearly not related to the investigational agent(s) or intervention: the AE has no temporal relationship to the administration of the investigational agent(s) or research intervention, and follows no known or suspected pattern of response, and an alternative cause is present.

AE = adverse event.

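### Treatment-related TEAEs are defined as possibly or probably related, so events graded definitely related are left out of the related-event tables; the TEAE definition also has a faulty 'and'

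*Combined protocol and SAP*

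**What the plan says.** Table 3 in section 9.5.1.10.3 gives the investigator four causality grades: "Definitely related", "Probably related", "Possibly related" and a fourth for unrelated events. The top grade is for an event with a temporal relationship that "follows a known pattern of response, and no alternative cause is present". The sentence introducing the table describes the assessment as a two-way choice between related and unrelated.

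Section 9.7.1.11 then sets out the tabulation. Subjects with TEAEs are to be "summarized by relationship to study drug (possibly related, probably related, and not related". The treatment-related subset is defined next: "Treatment-related TEAEs include those AEs considered by the investigator to be possibly or probably related to study treatment". That subset feeds two tables, one by system organ class and preferred term and one by maximum severity.

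The same section defines treatment emergence: "A TEAE is defined as an AE that emerges during treatment, having been absent at baseline and". Two bullets joined by 'or' follow: re-emergence of an event that was present earlier but had stopped before treatment, and worsening of a continuous event relative to its pretreatment state. Only treatment-emergent events enter the summary tables; the listings carry everything.

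**The concern.** The analysis text does not match the scale on which the data are collected, and the missing grade is the one with the clearest attribution. A programmer following section 9.7.1.11 would have no row for definitely related events and would leave them out of the treatment-related subset. Where such events occur, the error runs in one direction only: related incidence, or the maximum severity of related events, is understated or unchanged, never overstated.

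Safety and tolerability is a stated secondary objective, adverse events are one of the three named safety endpoints (section 9.7.1.3), and the synopsis promises a summary of TEAEs by relationship. Table 3 attributes events to the research intervention as well as to the agent, and subjects stay in the clinic for 2 hours after a single instillation, so some events could plausibly be graded definite.

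The wording of the TEAE definition matters for a wider reason: it decides what enters any AE summary table.

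**Working it through.** **Causality grades, side by side.** The plan gives no figure to reproduce here; the check compares categories.

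| Grade in Table 3 (9.5.1.10.3) | Row in relationship table (9.7.1.11) | Counted as treatment-related (9.7.1.11) |
|---|---|---|
| Definitely related | no | no |
| Probably related | yes | yes |
| Possibly related | yes | yes |
| Unrelated | yes | no (correctly) |

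The relationship table covers 3 of 4 grades. The treatment-related definition covers 2 of the 3 related grades. The uncovered grade is the same in both.

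**Effect on incidence.** For one arm, let N be the subjects in the safety set, R those with at least one definitely, probably or possibly related TEAE, and D those whose only related TEAEs are definite.

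- Incidence on the full scale: R/N
- Incidence as written: (R − D)/N
- Shortfall: D/N

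The synopsis plans arms of 60 (URG101, lidocaine) and 30 (placebo, heparin). With D = 1 the shortfall is 1/60 = 1.7 percentage points or 1/30 = 3.3 points.

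The documents give neither R nor D. As an assumption for illustration only, take N = 60 and R = 15, so that the full-scale incidence is 15/60 = 25%:

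| Assumed D | Reported incidence | Share of related subjects lost (D/R) |
|---|---|---|
| 0 | 15/60 = 25% | 0% |
| 3 | 12/60 = 20% | 20% |
| 6 | 9/60 = 15% | 40% |

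A subject who also has a probable or possible event still counts as related, so D is at most the number of subjects with any definite event.

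**Effect on severity.** A subject with a severe definite event and a mild possible event would appear in the related-by-severity table as mild.

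**TEAE definition, read literally.** The stem requires absence at baseline and, in addition, one of the two bullets.

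1. A plain new-onset event was absent at baseline but neither re-emerges nor worsens from a pretreatment state. It satisfies the stem and neither bullet, so it is not a TEAE.
2. A continuous event that worsens was present at baseline. It satisfies the second bullet but fails the stem, so it is not a TEAE either.
3. Only an event that had occurred earlier, stopped before treatment and then came back can meet both parts.

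With 'or' in place of 'and', all three kinds of event qualify.

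**The case against.** The strongest reply is that these are drafting slips with limited reach.

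- Definitely related events remain in the all-TEAE tables by system organ class, preferred term and severity, in the SAE summary if serious, and in the listings. No data are lost. This stands, with the qualification that the all-TEAE tables are a backstop only if the TEAE definition is not applied literally.
- The word 'include' in the treatment-related definition could be read as non-exhaustive, and the two-way lead-in to Table 3 would put a definite event on the related side. This is weak: the relationship categories are enumerated shortly before that definition, with the same omission.
- Section 9.7.1 defers detail to a separate SAP to be finalized before database lock, and that text is not among the documents. It could correct the error. The effect is therefore conditional on section 9.7.1.11 being followed as written.
- The size is unknown. The top grade requires that no other cause be present, which may be uncommon in catheterized patients who already have bladder pain, and some catheter discomfort precedes dosing. This stands, and it is why the incidence figures are only illustrative.
- Related incidence is a descriptive summary, and no test or stopping rule in the supplied text depends on it. This also stands.
- The literal TEAE definition defeats itself, so the intent is evidently 'or'. That is so, but the stated rule still gives the wrong set of events.

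**Conclusion.** The concern holds. Section 9.7.1.11 omits the strongest of the protocol's own causality grades from both the relationship table and the treatment-related definition, and no other text supplies the link. Followed as written, definitely related events drop out of three summaries: TEAEs by relationship, treatment-related TEAEs by system organ class and preferred term, and treatment-related TEAEs by maximum severity. The shortfall in related incidence is D/N per arm; its actual value depends on how often investigators use the top grade, which the documents do not indicate. The TEAE definition is also wrong as worded, and it governs all AE summary tables. Both are stated rules that give a wrong result. They should be corrected, although the underlying data and the listings are unaffected.

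**What to change.** In section 9.7.1.11:

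1. List the relationship categories as definitely, probably, possibly and not related.
2. Define treatment-related TEAEs as those graded definitely, probably or possibly related.
3. Reword the TEAE definition so that an event qualifies if it was absent at baseline and emerges during treatment, or re-emerges after having stopped before treatment, or worsens relative to the pretreatment state.

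In section 9.5.1.10.3, bring the two-way lead-in to Table 3 into line with its four grades; the protocol at present describes the scale with two, four and three levels. Carry the same wording into the separate SAP before database lock.

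The cost is a few words and one extra table row. No new data are needed, and nothing changes in trial conduct or sample size.
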